#### 16.1.4.5.4 Non-target lesion response

If no non-target lesions are identified at baseline (and therefore not followed throughout the study), the non-target lesion response at each assessment will be considered ‘not applicable (NA)’.

#### 16.1.4.5.5 Study/project specific programming

The standard analysis programs need to be adapted for each study/project.

#### 16.1.4.5.6 Censoring reason

In order to summarize the various reasons for censoring, the following categories will be calculated for each time to event variable based on the treatment completion page, the study evaluation completion page and the survival page.

For survival the following censoring reasons are possible:

- Alive
- Lost to follow-up

For PFS and TTP (and therefore duration of responses) the following censoring reasons are possible:

- Ongoing without event
- Lost to follow-up
- Withdraw consent
- Adequate assessment no longer available\*
- Event documented after two or more missing tumor assessments (optional, see [Table 16-5](#))
- Death due to reason other than underlying cancer
- Initiation of new anti-cancer therapy

\* Adequate assessment is defined in [Section 16.1.3.2.7](#). This reason is applicable when adequate evaluations are missing for a specified period prior to data cut-off (or prior to any other censoring reason) corresponding to the unavailability of two or more planned tumor assessments prior to the cut-off date. The following clarifications concerning this reason should also be noted:

- This may be when there has been a definite decision to stop evaluation (e.g. reason="Sponsor decision" on study evaluation completion page), when patients are not followed for progression after treatment completion or when only UNK assessments are available just prior to data cut-off).
- The reason "Adequate assessment no longer available" also prevails in situations when another censoring reason (e.g. withdrawal of consent, loss to follow-up or alternative anti-cancer therapy) has occurred more than the specified period following the last adequate assessment.
- This reason will also be used to censor in case of no baseline assessment.

### 16.3 Appendix 3: Drugs that are prohibited or to be used with caution

**Table 16-11 Capmatinib: drugs to be used with caution during co-administration**

Mechanism of Interaction	Drug Name
Strong CYP3A inhibitor	ombitasvir/paritaprevir/dasabuvir/ritonavir (Viekira Pak), indinavir/ritonavir, tipranavir/ritonavir, ritonavir, cobicistat, indinavir, ketoconazole, troleandomycin, telaprevir, danoprevir/ritonavir, eltegravir/ritonavir, saquinavir/ritonavir, lopinavir/ritonavir, itraconazole, voriconazole, mibepradil, posaconazole, telithromycin, grapefruit juice, conivaptan, nefazodone, neflifinavir, idelalisib, boceprevir, atazanavir/ritonavir, darunavir/ritonavir
Moderate CYP3A inducer	bosentan, dabrafenib, efavirenz, etravirine, genistein, modafinil, nafcillin, tipranavir/ritonavir, lopinavir, telotristat
CYP1A2 substrate with NTI	theophylline, tizanidine
P-gp substrates	afatinib, alfuzosin, aliskiren, alogliptin, ambrisentan, apixaban, apremilast, aprepitant, atorvastatin, boceprevir, bosentan, carvedilol, caspofungin, ceritinib, colchicine, cyclosporine, dabigatran, digoxin, docetaxel, doxepin, doxorubicin, eribulin, everolimus, fentanyl, fexofenadine, fidaxomicin, fluvastatin, fosamprenavir, idelalisib, iloperidone, indacaterol, irbesartan, lacosamide, lapatinib, levetiracetam, linagliptin, linezolid, loperamide, losartan, maraviroc, mirabegron, nadolol, naloxegol, nateglinide, nevirapine, nintedanib, olodaterol, paclitaxel, pantoprazole, paroxetine, pazopanib, posaconazole, pravastatin, proguanil, ranolazine, riociguat, risperidone, ritonavir, rivaroxaban, saquinavir, silodosin, simeprevir, simvastatin, sirolimus, sitagliptin, sofosbuvir, sorafenib, tacrolimus, telaprevir, tenofovir, ticagrelor, tipranavir, tolvaptan, topotecan, umeclidinium, valsartan, vardenafil, vincristine, voriconazole
BCRP substrates	atorvastatin daunorubicin, dolulegravir, doxorubicin, ethinyl estradiol, hematoporphyrin, imatinib, irinotecan, methotrexate, paritaprevir, pitavastatin, rosuvastatin, simvastatin, sofosbuvir, sulfasalazine, tenofovir, topotecan, venetoclax
Proton pump inhibitor	Dexlansoprazole, esomeprazole, lansoprazole, omeprazole, pantoprazole, rabeprazole
H 2 -receptor antagonists	cimetidine, famotidine, nizatidine, ranitidine
Antacids	aluminum carbonate, aluminum hydroxide, calcium carbonate, calcium hydroxide, bismuth subsalicylate
Source: The list is adapted from the Novartis Institutes for Biomedical PK Sciences internal memorandum (v01, 2018): drug-drug interactions (DDI) database, which is compiled primarily from the Indiana University School of Medicine's "Clinically Relevant" Table ( https://drug-interactions.medicine.iu.edu/Main-Table.aspx ), the University of Washington's Drug Interaction Database ( druginteractioninfo.org ), and the FDA's "Guidance for Industry, Drug Interaction Studies". NTI: narrow therapeutic index	

**Table 16-12 Capmatinib: prohibited drugs**

Mechanism of Interaction	Drug Name
Strong CYP3A4 inducer	carbamazepine, enzalutamide, lumacaftor, mitotane, phenobarbital, phenytoin, rifabutin, rifampicin, St. John's wort ( Hypericum perforatum )

Source: The list is adapted from the Novartis Institutes for Biomedical PK Sciences internal memorandum (v01, 2018): drug-drug interactions (DDI) database, which is compiled primarily from the Indiana University School of Medicine's "Clinically Relevant" Table (<https://drug-interactions.medicine.iu.edu/Main-Table.aspx>), the University of Washington's Drug Interaction Database ([druginteractioninfo.org](http://druginteractioninfo.org)), and the FDA's "Guidance for Industry, Drug Interaction Studies"

## 16.4 Appendix 4: Cockcroft-Gault formula for GFR estimate

Creatinine clearance will be calculated using the following formulas:

$$\text{Male GFR} = (140 - \text{age}) \times (\text{weight}) / (\text{sCr} \times 72)$$

$$\text{Female GFR} = (140 - \text{age}) \times (\text{weight}) \times 0.85 / (\text{sCr} \times 72)$$

GFR is Glomerular Filtration Rate in ml/min; Age is in years; Weight is Lean Body Mass in kilograms; sCr: is Serum Creatinine in mg/dl.

The formulas above should be altered in the following cases:

- Overweight (GFR >25 kg/m^2): Calculate based on adjusted body weight;  
Adjusted body weight = wtKgIdeal + 0.4 \* (wtKgActual - wtKgIdeal)
- Underweight: Use actual weight, Do not round up to Serum Creatinine (significantly underestimates GFR)
- Elderly: do not round up to Serum Creatinine (significantly underestimates GFR)
- Patients who had a limb amputation: measure 24 hour Creatinine Clearance

## Document History – Changes compared to previous final version of SAP

Finale

**List of abbreviations**

AE	Adverse event
AESI	Adverse Events of Special Interest
ALT	Alanine aminotransferase
ALP	Alkaline phosphatase
AST	Aspartate transaminase
ATC	Anatomical Therapeutic Classification
AUC	Area Under the Curve
bid	bis in diem/twice a day
BIRC	Blind Independent Review Committee
BOR	Best Overall Response
CI	Confidence Interval
CR	Complete response
CSR	Clinical Study report
CTC	Common Toxicity Criteria
CTCAE	Common Terminology Criteria for Adverse Events
DCR	Disease Control Rate
DI	Dose Intensity
DOIR	Duration of Intracranial Response
FAS	Full Analysis Set
eCRF	Electronic Case Report Form
IB	Investigator Brochure
LLOQ	Lower Limit of Quantification
MedDRA	Medical Dictionary for Drug Regulatory Affairs
NCI	National Cancer Institute
NSCLC	Non-Small Cell Lung Cancer
OIRR	Overall Intracranial Response
ORR	Overall Response Rate
PD	Progressive disease
PD	Protocol deviations
PDI	Planned Dose Intensity
PDS	Programming and data specification
PFS	Progression-Free Survival
PK	Pharmacokinetics
PR	Partial response
PT	Preferred Terms

[REDACTED]	[REDACTED]
RDI	Relative Dose Intensity
RECIST	Response Evaluation Criteria in Solid Tumors
SAE	Serious Adverse Event
SAP	Statistical Analysis Plan
SD	Stable disease
SOC	System Organ Class
SS	Safety Set
TBL	Total Bilirubin
TFLs	Tables, Figures, Listings
TTIR	Time to Intracranial Response
[REDACTED]	[REDACTED]
ULN	Upper Limit of Normality
WHO	World Health Organization

## 1 Introduction

This Statistical Analysis Plan (SAP) provides detailed statistical methodology for the analysis of data from the open label run-in (Part 1) of study INC280J12201 that will be presented in the final Clinical Study Report (CSR).

The output shells (in-text and post-text) accompanying this document can be found in the Tables, Figures and Listings (TFL) shells document. The specifications for derived variable and datasets can be found in the Programming Datasets Specifications (PDS) document. This version of the SAP is based on the Protocol version 01 released on 13-Oct-2021. All decisions regarding analysis, as defined in the SAP document, have been made prior to database lock of the Part 1 study data.

All changes to the planned analysis described in this document required before or after database lock will be made through an amendment or addendum, respectively. Note that obvious corrections will be made at the time of analysis to address minor formatting or spelling mistakes present in the TFL shells document without the need to amend.

The SAP, TFL shells and PDS documents may also serve as a reference for the creation of any outputs required outside of the CSR, e.g., IB updates, abstracts, posters, presentations, manuscripts and management updates. Data used for these analyses will have a status aligned to the database lock guidance.

[figure not shown]
### 1.1 Study design

This is a two-part, multicenter, phase II study to evaluate the efficacy and safety of capmatinib in combination with spartalizumab in treatment of naive patients with EGFR wt, ALK rearrangement negative advanced NSCLC, harboring MET exon 14 skipping (MET  $\Delta$ ex14) mutations.

The study consists of a single arm open label run-in part (Part 1) followed by a double-blind, placebo controlled, randomized part (Part 2). Following the study enrollment halt in Part 1, spartalizumab treatment has been discontinued and the randomized part (Part 2) will not be initiated.

An overview of the study design is provided in [Figure 1-1](#).

**Figure 1-1 Study design**

\*Following the study enrollment halt in Part 1, spartalizumab treatment has been discontinued and the randomized part will not be initiated.

[figure not shown]
**Part 1: Single Arm Run-in Part**

Approximately 30 subjects will be treated with the capmatinib and spartalizumab combination during the run-in part of the study (Part 1). The primary objective of Part 1 is to assess the ORR by investigator assessment as per RECIST 1.1 of the combination of capmatinib with spartalizumab.

Refer to [Figure 1-2](#) for an overview on the study design of Part 1.

**Figure 1-2 Study design for Part 1**

Following the approval of protocol amendment 01, tumor assessment FU and survival FU will not be performed.

[figure not shown]
EOT: end of treatment; FU: follow-up

**1.2 Study objectives and endpoints / Estimands**

Objectives and related endpoints for Part 1 are described in [Table 1-1](#) below.

**Table 1-1 Study objectives**

Objectives	Endpoints
Primary Objectives	Endpoints for primary objectives
To evaluate the anti-tumor activity of capmatinib in combination with spartalizumab	Overall Response Rate (ORR) by investigator assessment as per RECIST 1.1
Secondary Objectives	Endpoints for other secondary objectives

 
To assess safety and tolerability of capmatinib in combination with spartalizumab
 
To further evaluate the anti-tumor activity of capmatinib in combination with spartalizumab
 
To evaluate the PK of capmatinib and spartalizumab
 
	
 
Safety: incidence and severity of AEs and SAEs, changes in laboratory values, vital signs and ECGs. Any clinically significant lab, vital signs, ECG abnormalities will be captured as an AE
 
Tolerability: dose interruptions, reductions, and dose intensity
 
Disease Control Rate (DCR) and PFS by investigator assessment as per RECIST 1.1
 
Concentrations and derived PK parameters of capmatinib and spartalizumab
 

**1.2.1 Primary estimand**

The primary scientific interest is to estimate the effect of capmatinib in combination with spartalizumab in terms of overall radiological response by investigator assessment as per RECIST 1.1 in first line NSCLC with METΔex14 mutation.

The primary estimand is characterized by the following attributes:

1. Population: adult patients with NSCLC with METΔex14 mutation in first line setting. Further details on the population are provided in Section 5 of protocol amendment 01.
2. Treatment: capmatinib in combination with spartalizumab without any new anti-neoplastic therapy. Further detail about the treatment is provided in Section 6 of protocol amendment 01.
3. Variable: Best Overall Response (BOR) defined as the best response recorded from the start of the treatment until disease progression/recurrence by investigator assessment as per RECIST 1.1
4. Intercurrent events:
  - Discontinuation of spartalizumab for any reason (treatment policy strategy)
  - Discontinuation of tumor assessment follow up with approval of protocol amendment 01 (while on treatment strategy)
  - Any public health emergency as declared by local or regional authorities, e.g., pandemic, epidemic or natural disaster (treatment policy strategy)
  - New anti-neoplastic therapy (while on treatment strategy)

Details on how to handle the intercurrent events are provided in [Section 2.5.3](#).

5. Summary measure: Proportion of subjects with a confirmed CR/PR as BOR, with its corresponding two-sided exact binomial 95% CI.

## 2 Statistical methods

### 2.1 Data analysis general information

Study data will be analyzed by Novartis personnel using the most updated SAS® version in the GPS environment. For analyses using R and/or JAGS (e.g., Bayesian analysis) in the DaVinci environment will be used. PK parameters will be calculated using non-compartmental methods available in the most updated version of Phoenix WinNonlin.

Data from all participating centers in this protocol will be combined by part, so that an adequate number of subjects will be available for analysis. Data will be summarized using descriptive statistics (continuous data) and/or contingency tables (categorical data) for demographic and baseline characteristics, efficacy, safety, pharmacokinetic and pharmacodynamics measurements.

Study data in Part 1 will be reported in the final clinical study report (CSR) based on all subjects' data up to the time of completion of the study. There will be no additional CSR. The final CSR will include all outputs planned within the TFL shells document.

The part 1 of this study has one treatment arm: capmatinib + spartalizumab

**Qualitative data** (e.g., gender, race, etc.) will be summarized by means of contingency tables; a missing category will be included as applicable. Percentages will be calculated using the number of patients in the relevant population or subgroup as the denominator.

**Quantitative data** (e.g., age, body weight, etc.) will be summarized by appropriate descriptive statistics (i.e., mean, standard deviation, median, minimum, and maximum).

Screen failure patients are those who signed the informed consent, but never started the study treatment for any reason. For these patients, the eCRF data collected will not be included in analyses but will be reported in the CSR as separate listings.

#### 2.1.1 General definitions

##### 2.1.1.1 Investigational drug and study treatment

**Investigational drug** will refer to capmatinib or spartalizumab. The terms investigational drug and study drug are used interchangeably.

**Study treatment** will refer to capmatinib + spartalizumab.

##### 2.1.1.2 Date of first/last administration of study treatment

The date of first (last) administration of study treatment is derived as the start (end) date when a non-zero dose of either capmatinib or spartalizumab was administered and recorded on the study treatment eCRF.

### 2.1.1.3 Study day

The study day describes the day of the event or assessment date, relative to the reference start date. The study day is defined as:

- The date of the event (visit date, onset date of an event, assessment date etc.) – reference start date + 1 if event is on or after the reference start date.
- The date of the event (visit date, onset date of an event, assessment date etc.) – reference start date if event precedes the reference start date.

The reference date for all assessments (safety, efficacy, PK, etc) is the start of study treatment.

The study day will be displayed in the data listings. If an event starts before the reference start date, the study day displayed on the listing will be negative.

### 2.1.1.4 Time unit

A year length is defined as 365.25 days. A month length is 30.4375 days (365.25/12). If duration is reported in months, duration in days will be divided by 30.4375. If duration is reported in years, duration in days will be divided by 365.25.

### 2.1.1.5 Baseline

Baseline is the result of an investigation describing the “true” state of the subject before start of study treatment.

For all assessments (safety, efficacy, PK, etc), the last available assessment on or before the date of start of study treatment is taken as “baseline” assessment. In case time of assessment and time of treatment start is captured (e.g., pre-dose ECG), the last available assessment before the treatment start date/time is used for baseline.

For safety parameters (e.g., ECGs or vital signs), where study requires multiple replicates per time point, the average of these measurements would be calculated for baseline (if not already available in the database).

In rare cases where multiple measurements meet the baseline definition, with no further flag or label that can identify the chronological order, then the following rule should be applied: If multiple values are from the same laboratory or collected for ECGs or vital signs, then the last value should be considered as baseline.

If subjects have no value as defined above, the baseline result will be missing.

### Laboratory data

If labs with duplicate laboratory measurements taken at the last assessment date on or before the start date of study treatment, then the rule described below will be applied for the calculation of baseline:

1. For lab parameters with CTC grade, the lower CTCAE grade will be considered as the baseline value. For lab parameter with a bi-directional CTC grade, two baselines should be created; with the record with grade below 0 should be the baseline of the 'Hypo' parameter, and the other record should be the baseline for the 'Hyper' parameters.

2. For non-gradable labs:

- If both within normal range: take average value
- If one within normal range and the other outside: take the one within normal range
- If both outside normal range: take the one closest to the normal range

## ECGs

Baseline for ECG measurement is the average of the pre-dose replicate measurements on the baseline day. Unscheduled assessments will not be included in the calculation of the average. Study day 1 scheduled pre-dose ECGs will be considered to have been obtained prior to study drug administration if dosing time or ECG time is missing.

If a scheduled pre-dose measurement actually occurred post-dose, then the corresponding measurement will be treated and analyzed similar to an unscheduled post-dose measurement. For unscheduled assessments on study day 1, the assessment is classified as post-baseline.

If subject have no value as defined above, the baseline result will be missing.

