### 6.7.2.1 Capmatinib

Capmatinib tablets will be administered orally on a continuous twice daily (BID) dosing schedule, from Day 1 till Day 28 of each 28 day cycle. The starting dose of capmatinib will be 400 mg BID (total daily dose: 800 mg) on a flat scale of mg/day and not individually adjusted by weight or body surface area. A complete cycle of treatment is defined as 28 days of twice daily treatment with capmatinib. The investigator must instruct the subject to take the study drug exactly as prescribed.

- Subjects should take capmatinib tablets BID at approximately the same time each day starting on Cycle 1 Day 1.
- Each dose of capmatinib is to be taken with a glass of water (at least 8 ounces – approximately 250 mL) and consumed over as short a time as possible (i.e. not slower than approximately 1 tablet every 2 minutes).
- Subjects should be instructed to swallow the whole tablets and not to chew them.
- Capmatinib can be administered with or without food. The morning and the evening doses should be taken 12 ( $\pm$  4) hours apart, although a 12-hour interval is highly recommended. The morning dose should be taken at the same time each morning. If a dose is not taken within 4 hours of the planned dosing time, the missed dose should not be replaced.
- On days of co-administration of capmatinib with spartalizumab, subjects should be instructed to take the morning dose of capmatinib during the clinic visit, when instructed by site personnel. Capmatinib will be administered prior to spartalizumab/placebo infusion along with its pre-medication (if pre-medication is necessary).
- On days when PK blood samples are to be collected, subjects will be instructed to hold their dose until arrival at the study center. The pre-dose PK samples will be taken right before capmatinib administration. The exact time of drug administration should be recorded in the eCRF. If a subject vomits within 4 hours of capmatinib dosing, the time of vomiting will also be recorded in the eCRF.

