#### **8.4.6      ECG**

Electrocardiograms (ECGs) must be recorded after 10 minutes rest in the supine position. The preferred sequence of cardiovascular data collection during study visits is ECG collection first, followed by vital signs, and blood sampling.

Standard triplicate 12 lead ECG recording will be performed at the time points indicated in [Table 8-6](#). The individual ECGs should be recorded approximately 2 minutes apart.

The Fridericia QT correction formula (QTcF) should be used for clinical decisions. The mean QTcF value for each visit will be calculated from the triplicate ECGs for each subject.

For any ECGs with subject safety concerns, two additional ECGs must be performed to confirm the safety finding. A monitoring or review process should be in place for clinically significant ECG findings throughout the study and especially at baseline before administration of study treatment.

Clinically significant abnormalities must be recorded on the eCRF as either medical history/current medical conditions or adverse events as appropriate.

ECGs are to be collected with machines available at the site. Interpretation of the tracing must be made by a qualified physician and documented on the appropriate eCRF. Each ECG tracing should be labeled with the study number, subject initials (where regulations permit), subject number, date, and kept in the source documents at the study site. Clinically significant abnormalities present at screening should be reported on the appropriate eCRF. Clinically significant findings must be discussed with Novartis prior to enrolling the subject in the study. New or worsened clinically significant findings occurring after informed consent must be recorded as adverse events.

Additional, unscheduled, safety ECGs may be repeated at the discretion of the investigator at any time during the study as clinically indicated. Unscheduled ECGs with clinically significant findings should be collected in triplicate. Local cardiologist ECG assessment may also be performed at any time during the study at the discretion of the investigator.

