**Table 8-6 Local ECG collection plan**

Cycle	Day	Time	ECG Type
Screening		Anytime	12 Lead, triplicate
1	1	Pre-dose	12 Lead, triplicate
2	1	Pre-dose	12 Lead, triplicate
3	1	Pre-dose	12 Lead, triplicate
End of treatment		Anytime	12 Lead, triplicate
Unscheduled ECG		Anytime if clinically indicated	12 Lead, triplicate

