### 2.1.1.6 On-treatment assessment/event and observation periods

For all safety analyses, the overall observation period will be divided into three mutually exclusive segments:

- ***pre-treatment period***: from day of patient's informed consent to the day before first administration of study treatment
- ***on-treatment period***: from date of first administration of study treatment to 30 days after date of last actual administration of any study treatment (including start and stop date)
- ***post-treatment period***: starting at day 31 after date of last administration of study treatment

If dates are incomplete in a way that clear assignment to pre-, on-, post-treatment period cannot be made, then the respective data will be assigned to the on-treatment period.

Safety summaries will primarily include only data from the on-treatment period. Select summaries of related adverse events and death will be produced for the combined on-treatment and post-treatment periods of study treatment (see [Section 2.8.1](#) and [Section 2.8.2](#)).

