## 2.8.4 Other safety data

### 2.8.4.1 ECG data

12-lead ECGs including PR, QRS, QT, QTcF intervals, and HR will be obtained for each subject during the study. ECG data will be read and interpreted locally. The average of the ECG parameters at each assessment should be used in the analyses.

The number and percentage of subjects with notable ECG values will be presented.

- QT, or QTcF
  - New value of  $> 450$  and  $\leq 480$  ms
  - New value of  $> 480$  and  $\leq 500$  ms
  - New value of  $> 500$  ms
  - Increase from baseline of  $> 30$  ms to  $\leq 60$  ms
  - Increase from baseline of  $> 60$  ms
- HR
  - Increase from baseline  $> 25\%$  and to a value  $> 100$  bpm
  - Decrease from baseline  $> 25\%$  and to a value  $< 50$  bpm

- PR
  - Increase from baseline >25% and to a value > 200 ms
  - New value of > 200 ms
- QRS
  - Increase from baseline >25% and to a value > 120 ms
  - New values of QRS > 120 ms

ECGs collected during on-treatment will be summarized. The number and percentage of subjects with notable ECG values will be presented for the safety set. A listing of subjects with notable ECGs will be provided and value measure during the post-treatment follow up will be flagged in the listing.

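### Unscheduled day-1 ECGs are classed as post-baseline even when known to precede the first dose, so a pre-drug value could count as a new on-treatment finding

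*SAP*

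**What the plan says.** SAP 2.1.1.5 gives a general baseline rule. When assessment and dosing times are both captured, "the last available assessment before the treatment start date/time is used for baseline"; the SAP's own example is the pre-dose ECG.

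The ECG paragraph of the same section then adds four rules:

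- Baseline is the mean of the pre-dose replicates on the baseline day, and unscheduled ECGs do not enter that mean.
- A scheduled day-1 pre-dose ECG is presumed to be pre-dose if the ECG time or the dosing time is missing.
- Actual timing overrides the label for a scheduled ECG: "If a scheduled pre-dose measurement actually occurred post-dose, then the corresponding measurement will be treated and analyzed similar to an unscheduled post-dose measurement".
- ECGs taken off schedule that day get a blanket rule of their own: "For unscheduled assessments on study day 1, the assessment is classified as post-baseline".

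SAP 2.1.1.6 defines the on-treatment period as running "from date of first administration of study treatment to 30 days after date of last actual administration of any study treatment". The pre-treatment period ends the day before. SAP 2.8.4.1 states that "ECGs collected during on-treatment will be summarized" and lists notable categories, including new QT or QTcF values above 450 to 480 ms, above 480 to 500 ms and above 500 ms, as well as increases from baseline.

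On the protocol side, Table 8-6 schedules a triplicate ECG before dosing on Cycle 1 Day 1 and allows unscheduled ECGs "Anytime if clinically indicated". Section 8.4.6 adds: "For any ECGs with subject safety concerns, two additional ECGs must be performed to confirm the safety finding".

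**The concern.** The SAP uses recorded times in its general baseline rule, and again to move a mistimed scheduled ECG to the post-dose side. It does not use them for an unscheduled day-1 ECG, even when the time shows that no drug had been given. The missing-time clause does not help, because it covers scheduled ECGs only.

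Such ECGs are foreseeable. A worrying tracing at the scheduled pre-dose time on Cycle 1 Day 1 is an obvious reason for a repeat. Section 8.4.6 also asks for review of significant findings, particularly at baseline before treatment starts. It does not say whether the confirmatory ECGs come before or after dosing.

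ECG change is part of a named secondary safety endpoint (SAP Table 1-1). What is at stake is that a value obtained before any study drug could be tabulated as newly arising on treatment.

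**Working it through.** The plan states no figure on this point. The check traces one ECG through the rules and then bounds the effect.

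**Tracing an unscheduled ECG timed before the first dose on day 1**

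| Step | Rule | Result |
|---|---|---|
| Baseline mean | SAP 2.1.1.5, ECGs: unscheduled ECGs excluded | Not in baseline |
| Classification | SAP 2.1.1.5, ECGs: unscheduled on day 1 | Post-baseline |
| Missing-time clause | Scheduled ECGs only | Does not apply |
| General time-based rule | SAP 2.1.1.5 | Points the other way, but the ECG paragraph is more specific and would normally govern |
| Period | SAP 2.1.1.6: date-based | On-treatment |
| Notable counts | SAP 2.8.4.1: on-treatment ECGs, no stated exclusion of unscheduled ones | Could be counted |

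Even if a programmer followed the general rule, the date-based period in SAP 2.1.1.6 would still place the ECG on treatment.

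The last step is implied, not stated. SAP 2.8.3 expressly includes unplanned assessments in the laboratory summaries; SAP 2.8.4.1 says nothing either way for ECGs.

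**Size per subject**

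Protocol 4.1 reports 31 treated subjects in Part 1. One affected subject changes a category by at most 1/31 = 0.032, or 3.2 percentage points.

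**Example (assumed readings)**

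Take a scheduled pre-dose mean QTcF of 476 ms and a pre-dose unscheduled repeat of 484 ms. Baseline is 476 ms. The 484 ms reading is classed as post-baseline and on-treatment, and falls in the new-value category above 480 to 500 ms. The starting value lies above the 470 ms limit that Protocol 5.2 applies to the screening ECG.

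**Chance of crossing the 480 ms line, given that a repeat is taken**

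Let m be the scheduled mean and SD the standard deviation of the difference between two same-day triplicate means. The documents give no such SD; 5 to 10 ms is an assumption, and regression to the mean is ignored.

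P(repeat > 480 ms) = 1 − Φ((480 − m)/SD)

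| m (ms) | SD (ms) | (480 − m)/SD | Probability |
|---|---|---|---|
| 476 | 5 | 0.8 | 0.212 |
| 476 | 10 | 0.4 | 0.345 |
| 471 | 5 | 1.8 | 0.036 |
| 471 | 10 | 0.9 | 0.184 |

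Given a repeat, the chance is roughly 21 to 34% from 476 ms and 4 to 18% from 471 ms. If both readings fall in the same category, nothing is miscounted. These figures say nothing about how often repeats happen; that number is not in the documents and may be zero.

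**The case against.** The strongest reply is that this is a deliberate cautious convention. Leaving unscheduled ECGs out of the baseline mean stops selectively triggered readings from shifting baseline, and calling them post-baseline ensures that none drops out of safety review. The rule can add notable values but cannot hide one. That is a sound reason for the default when times are unknown. It does not justify reporting a reading known to precede the drug as an on-treatment event.

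The chain of conditions is also long: the ECG must be unscheduled, on day 1, before dosing, timed, in a higher category than the scheduled mean, and included in the table. This stands, and it limits the point to a minor one. So does the setting: a halted single-arm part, no hypothesis test, descriptive ECG output, and a listing of subjects with notable ECGs in which an odd day-1 case could be spotted.

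The numerical example is open to challenge:

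- The 470 ms limit applies to the screening ECG only, and the explicit repeat rule in Protocol Table 6-3 starts at 501 ms. No documented threshold forces a repeat at 476 ms.
- The two additional ECGs in Section 8.4.6 may simply complete a triplicate, whereas the example assumes a second triplicate mean.
- The probabilities rest on an assumed SD and on chosen starting values.

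The example should be read as an illustration of the mechanism. The classification problem does not depend on it.

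Clock time may also be unavailable, since Section 8.4.6 asks for the date on each tracing and does not list the time. In that case the proposed wording gives the same result as the present one.

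Finally, the fix leaves such an ECG inside the on-treatment period by date while excluding it from the on-treatment summaries. That is slightly untidy, but stating the exclusion explicitly avoids rewriting the period definitions.

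**Conclusion.** The concern holds. The sentence on unscheduled day-1 ECGs carries no time condition, conflicts with the SAP's time-based baseline rule, and is not corrected by the date-based periods or by the ECG summary section. A reading known to precede the first dose could therefore be counted as a new on-treatment value.

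The importance is low. The effect is at most 3.2 percentage points per affected subject per category, always towards overstating ECG findings, and the number of affected subjects is unknown and probably small. The conclusion assumes that unscheduled ECGs enter the notable-value counts, which SAP 2.8.4.1 implies but does not state. It concerns recorded pre-dose times only. The primary endpoint is untouched.

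**What to change.** Replace the sentence in the ECG part of SAP 2.1.1.5 with:

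> Unscheduled ECGs on study day 1 with a recorded time before the first dose are not classified as post-baseline; they are listed, excluded from the baseline average, and excluded from the on-treatment summaries and notable-value counts. If the ECG time or dosing time is missing, the unscheduled day-1 ECG is classified as post-baseline.

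The cost is one SAP sentence and one programming condition. The baseline average and the period definitions in SAP 2.1.1.6 stay as they are. Under the SAP introduction, the change is made by amendment before database lock or by addendum after it.

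Dosing time should often be available. For PK sampling days, Protocol 6.7.2.1 says: "The exact time of drug administration should be recorded in the eCRF". Tables 8-9 and 8-10, in force before amendment 01, put a pre-dose PK sample on Cycle 1 Day 1 for subjects given spartalizumab. The documents do not establish that every unscheduled ECG has a recorded time; where it has none, the current default continues.
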